- 7) Visual analog scales (100mm) will also be used to assess the degree to which various nicotine withdrawal symptoms may be experienced: depressed, clumsy, tired, anxious, happy, drowsy, sad, dizzy, alert, energetic, light-headed, irritable, frustrated, nervous, sad, desire to smoke, difficulty concentrating, increased appetite, hunger, weight-gain, difficultly sleeping, awakening at night, insomnia, restless, impatient, panicked, missing cigarettes, urge to smoke, disoriented. To be completed each visit (State). Completion time ~10 min.

Principal Investigator: [name].

Personality Scales

8) The Brief Externalizing Inventory (Hall et al., 2007), adapted from the full Externalizing inventory (Krueger et al., 2007), is a subset of 159 self-report items used to assess a range of behavioral and personality characteristics that have been attributed to a broad psychological construct termed externalizing. These characteristics include: physical/relational destructive-aggression, boredom proneness, irresponsibility, problematic impulsivity, drug and alcohol use or problems, theft, fraud, rebelliousness, alienation, and blame externalizing. A recent report demonstrated that participants rated as high externalizing displayed reduced amplitude ERNs in comparison to those with low externalizing scores (Hall et al., 2007). Thus, this measure may be a useful tool to account for variability in ERN amplitudes. To be completed once (Trait). Completion time: ~15min.

Date: March 2, 2022

- 9) The Temperament and Character Inventory (Cloninger et al., 1994) is a widely used test that assesses dimensions of personality (e.g., harm avoidance, novelty seeking, reward dependence, and persistence) that are considered to be related to monoaminergic function. To be completed once (Trait). Completion time: ~25min.
- 10) **Sensation Seeking Scale V** (SSS-V, Zuckerman et al., 1978) is a 40-item self-report questionnaire that assesses individual differences in sensation seeking. The scale consists of four subscales (Boredom Susceptibility [BS], Thrill and adventure seeking [TAS], Experience seeking [ES], and Disinhibition [Dis]) composed of 10-items each. To be completed once (Trait). Completion time: ~5-10min.
- 11) **Attitudes Towards Risk Questionnaire** consists of 34-self report items rated on a 5-point Likert scale that assess attitudes towards physical and psychological risk. To be completed once (Trait). Completion time: ~5-10min.
- 12) **Toronto Alexithymia Scale** (TAS-20): a 20-item self report questionnaire to assess emotional awareness To be completed once (Trait). Completion time: ~5min.
- 13) **Adult ADHD Self-Report Scale** (ASRS v1.1): This questionnaire is an 18-item checklist designed by the World Health Organization (WHO) and Workgroup on Adult ADHD to determine whether a participant is suffering from symptoms related to attention-deficit/hyperactivity disorder. To be completed once (Trait). Completion time: ~ 5 minutes.

Mood and Anxiety Scales

- 14) **The Positive and Negative Affect Schedule** (or similar self-rated questionnaire) is a 20-item scale composed of 10 items describing negative affect and 10 items describing positive affect. To be completed each visit (State). Completion time: ~5 min.
- 15) **Profile of Mood States (POMS)** measures present mood state by a list of adjectives on a 5-point Likert scale and measures six dimensions of affect, including tension-anxiety, depression-dejection, anger-hostility, vigor-activity, fatigue-inertia, and confusion-bewilderment. The measure has been shown to produce reliable and valid profiles of mood state (McNair et al., ; Cella et al., 1989). To be completed each visit (State). Completion time ~5min.

Principal Investigator: [name].

16) The State-Trait Anxiety Inventory Form Y (STAI) is an instrument for measuring anxiety in adults. The STAI differentiates between the temporary condition of "state anxiety" and the more general and long-standing quality of "trait anxiety." The essential qualities evaluated by the STAI-anxiety scale are feelings of apprehension, tension, nervousness, and worry. Form Y1 (State): To be completed each visit. Form Y2 (Trait): To be completed once. Completion time: ~5min each.

Date: March 2, 2022

- 17) **Beck Depression Inventory-II** (BDI-II: Beck et al., 1996): a brief self-administered inventory that assesses depressive symptoms both at the time of completion and in the preceding 7 days. The NIDA-IRP Critical Alert System will be activated in CDW to address critical responses to this questionnaire. To be completed once (Trait). Completion time: ~5 min.
- 18) **Beck Anxiety Inventory** (Beck et al., 1988): a brief inventory similar to the BDI-II that assesses symptoms of anxiety. To be completed once (Trait). Completion time: ~5 min.

Other Drug Use

19) **Drug Use Survey (DUS):** An interviewer-administered questionnaire designed to collect information regarding lifetime history of substance use. To be completed once (Trait). Completion time: < 40 minutes.

Other Questionnaires

20) **Menstrual Cycle History Questionnaire:** To be administered at the start of each visit. Menstrual cycle information can be used to better understand gender differences should they be apparent in this study. To be completed each imaging visit (State). Completion time ~2 min.

Date: March 2, 2022 Principal Investigator: [name].

24.7 tDCS Behavioral Pilot

Up to the first **25 non-smoking participants** will participate in the tDCS Behavioral Pilot. This pilot study will examine the effect of tDCS stimulation on behavioral outcomes on the Parametric Flanker, N-back, and Amygdala Reactivity tasks in the *mock scanner*. **All procedures will be done as currently approved in the main tDCS study, except without MRI** (i.e. in the mock scanner only) **or characterization questionnaires** (only the tDCS Blinding Questionnaire will be administered to this group).

The tDCS Pilot will consist of an Orientation Session (consent, nurse visit, and task training, questionnaires and tDCS toleration test; approximately 3.5 hours), and three Mock Scanner/tDCS sessions (same as below, *24.6:Arm Design and Procedures;* approximately 5 - 6 hours for three 1-hour mock scanner sessions separated by two 1-hour breaks). The orientation and each of the 3 mock scanner/tDCS sessions can be completed on the same or separate days, as NRB resources and participant scheduling allow.

Because the Pilot will not include real MRI, the mock/scanner tDCS session will not include time for resting scans or structural image scans. The order of tasks will be re-arranged to reflect this difference. Order of tasks does not affect participant safety or study design. tDCS stimulation parameters will be the same as currently approved in the main tDCS protocol.

During orientation, participants will complete the following questionnaires: (1) Brief Externalizing Inventory, (2) Temperament and Character Inventory, (3) Sensation Seeking Scale V, (4) State-Trait Anxiety Inventory Form Y (STAI), (5) Attitudes Towards Risk Questionnaire. These questionnaires collectively take ~60 min to complete. We may also analyze questionnaires completed by the participant, when the data was collected from Protocols 457 and/or 415. These data will be used to explore how individual differences affect response to tDCS.

Participants in the pilot will be compensated at the same rate as described in the main tDCS protocol, minus the MRI compensation. They will still receive the completion bonus. Pilot participants can make up to about \$258.50 if all sessions are completed on the same day. If sessions are completed on separate days, compensation will vary according to the remuneration table (see below, 24.18: Research and Travel Compensation).

Date: March 2, 2022 Principal Investigator: [name].

24.8. fMRI tasks

- 2. N-back Task to Engage the Executive Control Network: The n-back task is designed to parametrically manipulate working memory (WM) by asking participants to determine whether a given stimulus matches a stimulus presented in either the previous trial (1-back), 2 trials previously (2-back), or 3 trials previously (3-back). To control for attentional mechanisms, participants may also complete either 0-back trials, in which they simply respond to a predefined stimulus item; 1-back trials can also be chosen as a control condition. Variants of this task have been previously published (Cohen et al, 1994). The N-back task is known to engage the Executive Control Network (ECN) (Lerman et al 2014).

In the version of the task used for this study, we will choose only 2 of the parametric conditions, e.g. 1-back and 3-back. This will reduce the time required to complete the task so that it can fit within the relatively short 1-hour MRI scan session. The task will be given both during and after tDCS stimulation, to compare the "online" (during) and "offline" (after-effects) of stimulation on working memory.

3. Amygdala Reactivity Task to measure top-down control: Participants will complete a simple perceptual task previously shown to produce robust bilateral amygdala activity (Hariri et al., 2002; Pezawas et al., 2005; Foland-Ross et al., 2010), as well as top-down prefrontal regulation of amygdala reactivity (Hariri et al., 2002; Foland-Ross et al., 2010). This blocked fMRI paradigm consists of two experimental conditions: a face matching condition, and a sensorimotor control condition. During the emotion matching condition, participants view an array of 3 faces and their task is to select (via button press) one of the two faces that matches the identity of the target face. During the sensorimotor control task, participants view an array of 3 geometric shapes (circles, vertical and horizontal ellipses) and select one of the two shapes (bottom) that matches the target shape (top). Each block begins with a brief instruction screen ("match face" or "match shape"). During each emotion block different images selected from a standard set of pictures of facial affect (Ekman and Friesen, 1976), are presented. During the control blocks, different geometric shapes are presented in a pseudo-random order.

Principal Investigator: [name].

Date: March 2, 2022

24.9. Storage of data and Data Sharing Plan

The same as outlined for above in Section 5., Storage of data and samples and Section 6., Data Sharing Plan.

24.10. Risks/discomforts

tDCS: tDCS is a minimal risk procedure and side effects are mild, benign and transient. These may include itching, tingling, a reddening or a burning sensation of the skin underneath the stimulating electrode. These symptoms are deemed a discomfort in 10-14% of tDCS participants (Brunoni et al 2011). In order to further reduce these minimal risks, the impedance of the tDCS system will be continuously monitored throughout all sessions. Instead of the more popular sponge pads soaked in saline, bicarbon electrodes with a thick layer of conductive paste will be used to prevent drying of the electrodes during the scanning session. The stimulator will automatically turn off when the impedance value exceeds the critical range.

If discomforts occur, a decision will be made by the MAI or designate about whether the participant should complete the experiment. Headaches can also be a side effect of tDCS, and these subside with removal of the strap or with non-prescription medication. Non-prescription pain killers will be provided as decided on a case-by-case basis by the MAI.

Nicotine patch: the risks/discomforts of the nicotine patch are the same as listed in *Section 8.2. Nicotine Patch Administration*. Only the smoker group will receive nicotine patches. Nicotine dose will be individually tailored based on the average number of cigarettes smoked per day to better match daily nicotine intake. The following graded dosing scale will be used to individually tailor nicotine dose, it is identical to the scale found in *Section 4.1, Study Overview*:

"Nicotine administration during abstinence and scanning sessions. Two essential pharmacological issues that are of importance in the current design relate to participant's recent exposure to nicotine and to the selected dose administered to each participant. Doses will be individually tailored based on the average number of cigarettes smoked per day to better match daily nicotine intake (please see "Individually Tailored Nicotine Dose" in Section 1.5 above for justification). The dose for smokers consuming less than 10 cigarettes per day will be 14mg to start. If they are still experiencing cravings their dose will be increased to 21mg. The dose for smokers consuming 10-15 cigarettes per day will be a 21mg patch and this will be increased by 7mg for each additional 5 cigarettes/day (i.e., 21mg for individuals who smoked 10-15 cigarettes/day; 28mg for 15-20 cigarettes; 35mg for 20-25 cigarettes, and 42mg for more than 25 cigarettes). Nicotine patch doses up to 63mg/d have been shown to be safe and generally well-tolerated by smokers (Ebbert et al., 2007; Zevin, Jacob, & Benowitz, 1998)."

24.11. Outcome measures

There are no additional outcome measures beyond those described in the main protocol document (Sections 10.1 and 10.2).

Date: March 2, 2022 Principal Investigator: [name].

24.12. Statistical Analysis

The same as outlined above in Section 11, with the addition of the following power analyses.

Power Analysis.

General fMRI power. The same as outlined above in Section 11.4: "Since fMRI is the main outcome measurement utilized in the present protocol, the key power analysis pertains to the fMRI data. However, prospective power analyses for fMRI data are complicated for several reasons. First, fMRI data are analyzed in a hierarchal manner such that both the *intra*-participant variance from the time-course data and the inter-participant variance across individuals could affect statistical power. A large number of time points tend to mitigate effects of intra-participant variance, but temporal autocorrelation and scanner limitations limit the number of independent measurements per unit time and thus the number of independent time points that are collected. In addition, effect sizes and both types of variance will vary spatially. Because of this, a given study may have sufficient power to detect differences in some brain regions, but lack sufficient power in other regions where the null hypothesis is false. Finally, fMRI analysis consists of a very large number of non-independent multiple comparisons, greater than 1.5 million at the group level, necessitating correction methods less severe than a Bonferroni correction, as discussed above. Thus, a proper power analysis on fMRI data requires simulating all of these effects. Desmond and Glover (2002) have performed such a simulation. They show for a relatively modest signal change of 0.5% during a cognitive task and with an intra-participant standard deviation of 0.75% and an inter-participant standard deviation of 0.5%, that 11 participants are required for a power of 0.8 using p < 0.05. Using a false positive rate of p < 0.002, a level more consistent with a cluster size threshold to correct for multiple comparisons (Forman et al., 1995), and with the variances kept the same, approximately 21 participants are needed for an expected signal change of 0.5% and 11 participants for a signal change of 0.75%. For more than ~100 independent time points, power (and hence the intra-participant variance) is relatively independent of the number of time points (Desmond and Glover, 2002). All current analyses should fall within this range."

tDCS power. Based on laboratory experience and literature review, the effect size for tDCS is the smallest of the study manipulations. Therefore, sample sizes falling in the appropriate power range for tDCS will also fall within the appropriate range for other manipulations in this study. In a meta-analytic review of the effect of tDCS on behavioral performance in cognitive tasks, it was found that effect size (Cohen's d) for anodal stimulation was about 0.49 (CI: 0.26, 0.72) for tDCS vs sham stimulation (Jacobson, Koslowsky, & Lavidor, 2011). Cathodal tDCS has been found to produce less reliable effect sizes than anodal tDCS. There is no independent cathodal tDCS condition in this study, and we have calculated power for anodal tDCS stimulation. The direction of tDCS effect is not classically known across each of the task paradigms, thus a two-tailed dependent samples t-test will be used. Approximately 34 participants in each group (smoker and non-smoker) will be required to achieve a power of 0.8 when assessing the effect of anodal tDCS vs sham (α-level of 0.05, two-tailed, matched pairs t-test, assuming a medium effect size for anodal tDCS stimulation).

Accounting for non-completion and non-compliance, we are requesting a maximum accrual of $\underline{60}$ smokers (enrollees) and $\underline{55}$ non-smokers (enrollees), with expectation of $\underline{35}$ completers in the smoker group, and $\underline{45}$ completers in the nonsmoker group.

Date: March 2, 2022

Principal Investigator: [name].

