To understand the effect of anodal stimulation of the dlPFC, and cathodal stimulation of the vmPFC, we will compare the following tDCS montages: (1) anodal left-dlPFC + cathodal right-vmPFC stimulation, with anode over the left dlPFC and cathode over the right-vmPFC; (2) cathodal left-dlPFC + anodal right-vmPFC stimulation, in which polarity is reversed between the two electrodes, and (3) sham stimulation.

Sub-Aim 1.1: To determine the effect of tDCS stimulation on the Executive Control Network (ECN) and cognitive control during nicotine withdrawal. Resting state connectivity, behavioral tasks and functional imaging will be used to measure the strength of the ECN and cognitive control mechanisms in response to excitatory tDCS stimulation of the left dlPFC, a cortical node of the ECN.

Hypothesis 1.1.1. Anodal-dlPFC tDCS will strengthen the within-network connectivity of the Executive Control Network compared to sham as measured by resting state functional connectivity in *abstinent smokers* > *sated smokers* > *healthy controls*. Cathodal-dlPFC tDCS will have the inverse effect on ECN rsFC.

Hypothesis 1.1.2. Anodal-dlPFC tDCS will improve reaction time and response accuracy on cognitive control tasks (Parametric Flanker, Amygdala Reactivity Task, and N- back) in *abstinent smokers* > *sated smokers* > *healthy controls*. The improved behavioral performance will be correlated with increased BOLD signal in nodes of the ECN. Cathodal-dlPFC tDCS will have the inverse effect on BOLD signal and behavior.

Sub-Aim 1.2: To determine the effect of tDCS stimulation on the Default Mode Network (DMN) during nicotine withdrawal. Resting state connectivity, behavioral tasks and functional imaging, magnetic resonance spectroscopy, and white matter integrity will be used to measure the strength of the DMN and cognitive control mechanisms in response to excitatory tDCS stimulation of the left dlPFC, a cortical node of the ECN, and inhibitory tDCS stimulation of the left vmPFC, a cortical node of the DMN.

Hypothesis 1.2.1. Cathodal-vmPFC tDCS will weaken the within-network connectivity of the Default Mode Network as measured by resting state functional connectivity in *abstinent smokers* > *sated smokers* > *healthy controls*. Anodal-vmPFC tDCS will have the inverse effect on DMN rsFC.

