Hypothesis 1.2.2. Cathodal-vmPFC tDCS will improve reaction time and response accuracy on cognitive control tasks (Parametric Flanker, Amygdala Reactivity Task, and N-back) in abstinent smokers > sated

CNS IRB Protocol Template (rev. 16Jun11)

Principal Investigator: [name].

smokers > *healthy controls*. The improved behavioral performance will be correlated with greater BOLD deactivation in nodes of the DMN during these tasks. Anodal-vmPFC tDCS will have the inverse effect on BOLD signal.

Sub-Aim 1.3: To determine the effect of tDCS stimulation on the Salience Network (SN) and its connectivity with the ECN and the DMN.

Hypothesis 1.3.1. Anodal-dlPFC tDCS will strengthen the between-network connectivity of the Executive Control Network to the Salience Network compared to sham as measured by resting state functional connectivity in *abstinent smokers* > *sated smokers* > *healthy controls*. Cathodal-dlPFC tDCS will have the inverse effect on ECN-SN rsFC.

Hypothesis 1.3.2. Cathodal-vmPFC tDCS will weaken the between-network connectivity of the Default Mode Network to the Salience Network as measured by resting state functional connectivity in *abstinent smokers* > *sated smokers* > *healthy controls*. Anodal-vmPFC tDCS will have the inverse effect on DMN-SN rsFC.

Hypothesis 1.3.3. Anodal-dlPFC + Cathodal-vmPFC tDCS will improve BOLD reactivity in nodes of the Salience Network in tasks that are known to those nodes (e.g. the insula in the Parametric Flanker Task). Cathodal-dlPFC + Anodal-vmPFC will have the inverse effect on BOLD reactivity in the SN.

Aim 2: To compare the effects of tDCS stimulation parameters on behavior, resting state functional connectivity, and BOLD fMRI signal.

Sub-Aim 2.1: To compare the effect of tDCS stimulation on a working memory task given during stimulation (online) and after stimulation (offline).

Hypothesis 2.1.1: Active tDCS stimulation will provide greater benefit on accuracy and response time, and increase BOLD activation in the ECN to a greater degree, during the "online" working memory task than during the "offline" working memory task.

Alternative Hypothesis 2.1.1(a): Active tDCS stimulation will provide greater the same degree of benefit on accuracy and response time, and increase BOLD activation in the ECN to the same degree, during the "online" working memory task as during the "offline" working memory task.

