24.6. Arm design and procedures

We will recruit smokers and matched non-smokers for a randomized, sham-controlled crossover study of 3 conditions of tDCS: (1) anodal left-dlPFC + cathodal right-vmPFC stimulation, with anode over the left dlPFC and cathode over the right-vmPFC; (2) cathodal left-dlPFC + anodal right-vmPFC stimulation, in which polarity is reversed between the two electrodes, and (3) sham stimulation. These are summarized in Table 1. Because tDCS is MRI scanner-compatible (Wörsching et al. 2016; Johnstone, Hinson, & Stagg 2016; Downar & Davis 2015; Antal et al. 2014), all tDCS sessions will be performed "online" while the participant is in the MRI scanner. The tDCS model we will use is the *neuroConn DC-Stimulator MR* (neuroCare Group GmbH, Munchen, Germany).

Date: March 2, 2022

Smoking subjects will attend a total of 3 visits (Orientation, MRI/tDCS +Nicotine patch, and MRI/tDCS + Placebo patch), and non-smoking subjects will attend a total of 2 visits (Orientation and MRI/tDCS without patch). Each visit day will consist of the 3 independent MRI/tDCS sessions (**Figure 1**), and the nature of the tDCS condition will be double blinded and randomized. The 3 MRI/tDCS sessions will correspond with the 3 tDCS conditions: (1) anodal left-dlPFC + cathodal right-vmPFC; (2) cathodal left-dlPFC + anodal right-vmPFC; and (3) sham.

Each tDCS stimulation will last approximately 25 minutes, and will occur concurrently while the participant is inside the MRI scanner. MRI/tDCS sessions will last about 60-100 minutes, with scans taken before, during, and after the tDCS stimulation (**Figure 2**). Each of the 3 MRI/tDCS sessions has a "core block" of scans that is the same across sessions. These include the Resting scan during tDCS stimulation, and task scans during and after stimulation. The "core block" takes about 1 hour to complete.

In addition to the "core block", the first MRI/tDCS session of the day contains a Baseline Resting Scan, and at least one of the MRI/tDCS sessions will contain a DTI scan (unless tDCS is found to induce artifact in DTI, see note on next page). The resting and DTI scans each add ~10-15 minutes to the total session time. The addition of these scans will not affect participant safety or study design. Only 1 DTI scan is needed per person, and would only be repeated if the first scan was of poor quality.

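### The dlPFC and vmPFC hypotheses of the tDCS arm rest on one paired montage, so no planned contrast can credit an effect to either site

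*Combined protocol and SAP*

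**What the plan says.** Section 24.6 lists the three tDCS conditions as "1) anodal left-dlPFC + cathodal right-vmPFC; (2) cathodal left-dlPFC + anodal right-vmPFC; and (3) sham". Table 1 in that section repeats the list for smokers under placebo patch, smokers under nicotine patch, and non-smokers. Aim 1 in Section 24.3 describes the first active montage as "stimulation, with anode over the left dlPFC and cathode over the right-vmPFC" and the second as one "in which polarity is reversed between the two electrodes".

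The hypotheses that follow are labelled by single site. Hypothesis 1.1.1 says "Anodal-dlPFC tDCS will strengthen the within-network connectivity of the Executive Control Network compared to sham as measured by" resting-state connectivity. Hypothesis 1.1.2 begins "Anodal-dlPFC tDCS will improve reaction time and response accuracy on" three named cognitive control tasks. Hypothesis 1.2.2 says "Cathodal-vmPFC tDCS will improve reaction time and response accuracy on cognitive control tasks", and names the same three tasks with the same ordering of groups. Hypotheses 1.2.1, 1.3.1 and 1.3.2 follow the same pattern for connectivity outcomes. Hypothesis 1.3.3 is different: it names both electrodes together.

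Section 24.12 carries over the analyses of Section 11 and adds power calculations. It states: "There is no independent cathodal tDCS condition in this study, and we have calculated power for anodal tDCS stimulation". It then gives about 34 participants per group for anodal stimulation versus sham, using a two-tailed matched-pairs t-test at 0.05, power 0.8 and a medium effect, beside a meta-analytic d of about 0.49 (CI 0.26 to 0.72).

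**The concern.** The power text recognises that cathodal stimulation is never given on its own. The same is true of anodal stimulation, because each active session has one electrode on each site. The labels anodal-dlPFC and cathodal-vmPFC therefore name one experimental condition, and the reversed labels name one other. Six hypotheses nevertheless credit one site or the other.

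This matters for what the arm can conclude. Sections 1.6 and 24.2 present the dlPFC and the vmPFC as two candidate targets for a cessation aid, with an excitatory role for one and an inhibitory role for the other. A montage effect read as evidence about one of these targets would be a causal statement that the design cannot identify. For behaviour, two hypotheses would also stand or fall on one test.

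**Working it through.** **1. The plan's own figure.** For a paired t-test with n participants, the noncentrality is d√n on n - 1 degrees of freedom. With d = 0.50 and n = 34 it is 0.50 × √34 = 2.92. The exact two-sided power at 0.05 is 0.808, and 34 is the smallest n that reaches 0.80. The stated figure reproduces. (With d = 0.49 the answer is 35.) It covers one contrast: the first active montage versus sham.

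**2. Can the sites be separated?** Code each site +1 for anodal, -1 for cathodal and 0 for sham.

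| Condition | Intercept | dlPFC (D) | vmPFC (V) |
|---|---|---|---|
| Sham | 1 | 0 | 0 |
| Montage 1 | 1 | +1 | -1 |
| Montage 2 (reversed) | 1 | -1 | +1 |

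V = -D in every row, so the correlation of D and V is -1 and the rank is 2, not 3. With mean response μ + βD·D + βV·V:

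- Montage 1 - sham = βD - βV
- Montage 2 - sham = -(βD - βV)
- Montage 1 - Montage 2 = 2(βD - βV)

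Only βD - βV is estimable. For example, (βD, βV) = (0.5, 0), (0, -0.5) and (0.25, -0.25) all give +0.5 for montage 1 and -0.5 for montage 2.

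This coding assumes that cathodal stimulation has the opposite effect to anodal at the same site. Dropping that assumption does not help. With a separate indicator for each site and polarity there are five columns including the intercept, and the rank is 3. The anodal-dlPFC column is identical to the cathodal-vmPFC column, and the cathodal-dlPFC column to the anodal-vmPFC column. The same three rows recur within each patch condition and in non-smokers, so the predicted group ordering adds no information about site. As a check on the algebra only, adding rows in which one site is active alone restores rank 3.

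**3. What each pair of hypotheses shares.** The comparator is taken to be sham, as 1.1.1, 1.3.1 and Section 24.12 state; the other hypotheses do not name one.

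| Pair | Outcome credited to dlPFC | Outcome credited to vmPFC | Same contrast? | Same outcome? |
|---|---|---|---|---|
| 1.1.1 / 1.2.1 | within-ECN connectivity | within-DMN connectivity | yes | no |
| 1.1.2 / 1.2.2, behaviour | reaction time, accuracy, three tasks | reaction time, accuracy, same tasks | yes | yes |
| 1.1.2 / 1.2.2, BOLD | ECN activation | DMN deactivation | yes | no |
| 1.3.1 / 1.3.2 | ECN-SN connectivity | DMN-SN connectivity | yes | no |

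Only the second row is literally one test. In the other rows a different outcome does not identify the site. The caption to Figure 1a calls the ECN and DMN anticorrelated, and Alternative Hypothesis (1) supposes that each network weakens the other. On the protocol's own account, a change in either network could start from either electrode.

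**4. Reversed polarity.** For the reversed montage, 1.1.2 predicts an inverse effect on both BOLD and behaviour, whereas 1.2.2 predicts it on BOLD only. One condition thus carries two different statements.

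**5. Other analyses.** Section 11.2 contains no tDCS contrast, and Section 24.12 adds only power. The current-flow regression in Hypothesis 4.1 is post hoc and names both nodes together.

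**The case against.** The protocol does not ignore the pairing. Aim 1 defines both montages as electrode pairs just before the hypotheses, and Sub-Aim 1.2 measures the DMN in response to stimulation of both nodes. Hypothesis 1.3.3 and Alternative Hypothesis (2) treat the montage as one intervention. The single-site labels can be read as shorthand for the montage, named after the node relevant to the outcome. This is fair. It shows that the remedy fits the authors' own understanding, but it leaves six hypotheses worded as claims about one site.

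Four stronger readings are tempting, and the documents do not support them:

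- *One result would confirm both mechanisms throughout.* This is true only for reaction time and accuracy in 1.1.2 and 1.2.2, for the first montage versus sham. The connectivity pairs and BOLD clauses have separate outcomes that can succeed or fail separately.
- *The plan intends to report or count one finding twice.* Sections 24.11 and 24.12 give no rule for interpretation or for counting supported hypotheses. The risk comes from the labels, not from a stated intention.
- *The sample size is wrong.* It reproduces, and the montage effect it covers is validly estimable.
- *The effect size comes from studies of anodal stimulation alone.* Section 24.12 says only that it is for anodal stimulation. Whether those studies also had an active cathode cannot be known from the documents.

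**Conclusion.** The point holds in a limited form. In this design the effects of anodal dlPFC and cathodal vmPFC are completely aliased (rank 2 of 3, or 3 of 5 with free polarity effects), whatever the number of participants. Hypotheses 1.1.1, 1.1.2, 1.2.1, 1.2.2, 1.3.1 and 1.3.2 therefore claim more than any planned contrast can identify. One duplication is exact: the reaction-time and accuracy predictions of 1.1.2 and 1.2.2 for the first montage versus sham are the same test on the same data. The conclusion rests on the three conditions in Section 24.6 and Table 1, on sham as comparator, and on the absence of any site-separating analysis in Sections 11 and 24.12. Taking the reversed montage as comparator would not change it. The montage-level effect and the 34 per group stand.

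**What to change.** 1. In Section 24.3, restate 1.1.1, 1.1.2, 1.2.1, 1.2.2, 1.3.1 and 1.3.2 as effects of the combined montage (anode on left dlPFC with cathode on right vmPFC) versus sham, with reversed polarity as the comparison condition. Hypothesis 1.3.3 already pairs the electrodes this way.
2. Keep the network-specific connectivity and BOLD outcomes as separate tests, but state the shared reaction-time and accuracy prediction once, test it once and count it once.
3. Reconcile the reversed-polarity predictions of 1.1.2 and 1.2.2 as to whether behaviour is included.
4. Add a sentence to Section 24.12 that effects are attributed to the montage and not to either node.
5. In the power paragraph, describe the powered contrast as montage versus sham, using an effect size reported for anodal stimulation. The 34 per group does not change.

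In the same edit, Sub-Aim 1.2 refers to the left vmPFC while the montage definitions refer to the right; these passages must be reconciled.

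The cost is wording only: no new participants, sessions or conditions. What is given up is the claim to site-specific effects, which the data could not have supported.
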